A sample size of 7 patients provides ~95% power at 1-sided alpha of 0.05 and ~91% power at 1-sided alpha of 0.025, to yield a statistically significant difference compared to a historical control rate of 10%, based on a one-sample test, assuming a 66% response rate in patients who are treated with setmelanotide. The Sponsor has chosen 1-sided, alpha=0.05 as the scientific success criterion associated with the primary analysis.

Although these data suggest that powering the study for the primary endpoint will require a minimal number of patients (N<10), the size of the trial is also a function of the rarity of BBS and AS and a desire to better understand the effect of setmelanotide in these patient populations. Hence, approximately 30 patients (including 6 AS patients) are planned to be enrolled in the study. This number is suitable for a single pivotal trial to support the indications in BBS and AS and to provide robust information for both the between group analysis of the placebo-controlled, double-blinded period and the one-sample comparison to the historical control response rate after the planned 38 week open-label treatment period.

The primary analysis on the primary efficacy endpoint will be based on the \geq 12 yo FAS. By nature of the study design, a small percentage of patients who are randomized into the placebo arm may have less than \sim 52 weeks of setmelanotide treatment by the timing of the primary analysis (end of Period 2); hence, a linear model based extrapolation will be used to impute their measurements after \sim 52 weeks setmelanotide treatment for the primary analysis. In general, missing values unrelated to study treatment (eg, due to lost to follow-up or missed visit) will also be imputed with the linear model based extrapolation, but missing values due to treatment-related reasons (eg, lack of efficacy or AEs) will be imputed as treatment failures. A data snapshot will be taken for the primary analysis, and a supplemental supportive analysis will be performed on a locked database following study completion.

TABLE OF CONTENTS

CLINIC	AL STUDY PROTOCOL	1
APPROV	VAL SIGNATURE PAGE	2
INVEST	IGATOR STATEMENT	3
CLINIC	AL STUDY SYNOPSIS	4
TABLE	OF CONTENTS	10
List of Ta	ables	15
List of Fi	gures	15
LIST OF	ABBREVIATIONS	16
1.	INTRODUCTION	20
1.1.	Purpose of Study	20
1.2.	Overview of Bardet Biedl and Alström Syndromes	20
1.2.1.	Bardet Biedl Syndrome	20
1.2.2.	Alström Syndrome	21

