8.5. Efficacy Analyses

8.5.1. Primary Efficacy Analysis

The primary efficacy endpoint is the proportion of patients (≥ 12 years of age at baseline) who achieve a $\geq 10\%$ reduction from baseline in body weight (ie, are 'responders') after ~ 52 weeks of treatment with setmelanotide. The statistical hypothesis for the primary efficacy endpoint is:

H0:
$$p_t \le 10\%$$
 vs H1: $p_t > 10\%$

where p_t is the response rate after \sim 52 weeks of setmelanotide treatment (ie, \sim Week 53 for patients randomized to setmelanotide and \sim Week 66 for patients randomized to placebo).

The subgroup of patients ≥12 years of age was selected for the primary analysis because this is the group of patients for whom the interpretation of weight loss is most straightforward. Normal weight gain that accompanies increases in patient height during childhood growth and development can confound interpretation of the efficacy of weight loss drugs (Kelly 2016).

The statistical hypothesis will be tested using an exact binomial test, at a 1-sided 0.05 significance level. The 1-sided 0.05 significant level was chosen based on the small sample size due to the rarity of the disease. A 2-sided 90% confidence interval (CI) will be calculated using the exact Clopper-Pearson method. The success criterion for the primary hypothesis requires the rejection of the null hypothesis at the 1-sided 0.05 significance level. The statistical criterion

corresponds to the 2-sided 90% CI for setmelanotide of the response rate excluding 10% (ie, lower bound of the CI >0.10).

The primary analysis on the primary efficacy endpoint will be based on the ≥12 yo FAS. Timing of the analysis and general missing data handling principles are described in Section 8.4. A sensitivity analysis based on data as observed (ie, no imputation on missing values) will be provided. Additional sensitivity analysis based on Per-Protocol Analysis Set will be explored as appropriate.

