4.3.1. Primary Efficacy Analysis

The primary efficacy analysis on the primary efficacy endpoint will be conducted in patients ≥12 years of age (at informed consent) in the FAS population.

[figure not shown]
The primary efficacy endpoint is the proportion of patients (≥ 12 years of age) who achieve a $\geq 10\%$ reduction in body weight from baseline after ~ 52 weeks of treatment. The null hypothesis (H0) to be tested is that the proportion of patients treated for ~ 52 weeks who achieve $\geq 10\%$ reduction in body weight from baseline is less than or equal to a historical control rate of 10%. The alternative hypothesis (H1) is that the proportion is greater than a historical control rate of 10%:

H0: $p_t \le 10\%$ vs H1: $p_t > 10\%$

where p_t is the response rate after ~52 weeks of treatment.

Please note that there are two different uses of "10%" above, which is explained here for clarity:

- The use of "10%" in the endpoint definition is the **response criteria** for an individual patient. If a patient achieves a ≥10% reduction from baseline in body weight, the patient will be categorized as a responder in this analysis. Otherwise, the patient will be categorized as a non-responder.
- The use of "10%" as the historical control **rate** is the historical reference/control response rate to be statistically compared to the observed response rate in patients treated with setmelanotide. The observed response **rate** of setmelanotide will be calculated with the number of responders (using the above 10% endpoint definition) divided by the number of total patients.

The primary endpoint will have binomial proportions calculated for each of the 100 imputed datasets. The outcomes from the 100 imputed datasets will be combined using Rubin's Rule to provide an overall estimate against the null hypothesis with corresponding confidence intervals and p-value (Little and Rubin, 2002). The 1-sided 0.025 significant level was chosen based on the small sample size due to the rarity of the disease. The success criterion for the primary hypothesis requires the rejection of the null hypothesis at the 1-sided 0.025 significance level. The statistical criterion corresponds to the 2-sided 95% CI for setmelanotide of the response rate excluding 10% (i.e., lower bound of the CI >0.10).

This analysis may be repeated on the following analysis sets: DUS, PP at EOP2, SH, AG, as appropriate.

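### SAP 4.3.1 swaps the protocol's exact binomial test for Rubin-combined proportions without naming the variance or a rule for 0% and 100% response; on the natural Wald reading the test is conservative and its interval generally under-covers

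*SAP*

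**What the plan says.** Protocol 8.5.1: "The statistical hypothesis will be tested using an exact binomial test, at a 1-sided 0.05 significance level". The interval matches the test: "A 2-sided 90% confidence interval (CI) will be calculated using the exact Clopper-Pearson method".

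SAP 4.3.1 names neither method. It says "The primary endpoint will have binomial proportions calculated for each of the 100 imputed datasets", and the results are combined by Rubin's Rule "to provide an overall estimate against the null hypothesis with corresponding confidence intervals and p-value". Success is one-sided p below 0.025, which the section equates with a two-sided 95% lower limit above 10%. SAP 3.10.1 names PROC MIANALYZE for the pooling. The public text gives no within-imputation variance, transformation, degrees of freedom, or rule for a proportion of 0 or 1.

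Four other places bear on the point:

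- SAP 1.1.1 lets the SAP modify and override the protocol, and fixes the pivotal cohort at 38 patients of all ages (32 BBS, 6 AS).
- SAP 3.10.1 expects few placebo-arm patients to need administrative imputation. SAP 3.10.2 sets other missing values to baseline, which makes those patients non-responders in every imputed dataset.
- SAP 4.3.2 analyses the 25% hunger-responder endpoint in the same way as the primary endpoint.
- SAP 3.8.1 and Table 3 carry the primary endpoint into BBS, AS and paediatric subgroups.

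**The concern.** Rubin's rules take an estimate and a standard error from each dataset and return a test based on a normal or t distribution. With few imputed values the between-imputation variance is small, so the result is close to a plain large-sample test of one proportion. That approximation is weak for a few dozen patients and a null of 10%, and the answer depends on which standard error is used. The SAP leaves this open in the trial's success criterion and, through it, in the hunger-responder endpoint and any subgroup intervals. A borderline result could turn on a programming default, and the reported interval may not have its stated coverage even when the decision is not in doubt.

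**Working it through.** **Inputs.** The null rate is p0 = 0.10 (SAP 4.3.1: the proportion "is less than or equal to a historical control rate of 10"%). The design rate is 0.66 (protocol synopsis, Statistical Considerations: "assuming a 66% response rate in patients who are treated with setmelanotide"). The level is one-sided 0.025 (SAP 3.2 and 4.3.1). The number aged 12 or over is not in the documents, so n = 24 to 38 is assumed. Both methods are compared at 0.025, to separate the change of method from the SAP's change of level.

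**The plan's own figure.** The synopsis states: "A sample size of 7 patients provides ~95% power at 1-sided alpha of 0.05 and ~91% power at 1-sided alpha of 0.025". An arcsine approximation reproduces both values: h = 2·arcsin√0.66 − 2·arcsin√0.10 = 1.253, and Φ(1.253·√7 − z) = 95.3% and 91.2%. The exact test gives 95.1% at 0.05 (3 or more of 7, size 0.0257). At 0.025 it needs 4 of 7 and gives 81.6%. This does not matter at the enrolled size.

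**Three rules.** With x responders and p̂ = x/n:

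- Exact: reject if P(X ≥ x | n, 0.10) ≤ 0.025.
- Wald (Rubin's rules with negligible between-imputation variance): reject if p̂ − 1.96·√(p̂(1−p̂)/n) > 0.10.
- Null variance: reject if (p̂ − 0.10)/√(0.09/n) > 1.96.

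| n | Exact needs | Wald needs |
|---|---|---|
| 24-25 | 7 | 7 |
| 26-29 | 7 | 8 |
| 30-31 | 8 | 8 |
| 32-36 | 8 | 9 |
| 37-38 | 9 | 9 |

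The two differ at 9 of the 15 sizes. Attained Wald size over n = 24 to 38 is 0.3% to 1.1%.

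**Worked example, 7/28.** p̂ = 0.25 and the standard error is √(0.25·0.75/28) = 0.0818. The Wald limits are 0.25 ± 1.96·0.0818 = 9.0% to 41.0%, with z = 0.15/0.0818 = 1.83 and p = 0.033: failure. Exact p = P(X ≥ 7 | 28, 0.10) = 0.018, with Clopper-Pearson limits 10.7% to 44.9%: success.

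**Size and power at n = 28.** Wald: P(X ≥ 8) is 0.5% at a true rate of 10% and 64% at 30%. Exact: P(X ≥ 7) is 1.8% and 78%. At 40% the powers are 93% and 97%. At 66% both exceed 99.9%.

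**Null-variance reading.** At n = 28, 6 responders suffice: (0.2143 − 0.10)/√(0.09/28) = 2.02. The size is P(X ≥ 6) = 5.5%. Size exceeds 2.5% at 13 of the 15 sizes, all but n = 29 and 36. The unstated variance therefore moves the n = 28 threshold between 6 and 8, against 7 for the exact test.

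**Coverage of the nominal 95% Wald interval.** At true rates of 10%, 20%, …, 70% and 66%, summing binomial probabilities over all outcomes gives about 91% to 95% at n = 28 and 82% to 95% at n = 31. Rates between these can be worse. At n = 28 and a true 11%, outcomes 0 and 1 both miss, because the upper limit for 1/28 is 10.4%. P(X ≤ 1) = 0.17, so coverage is below 83%.

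**With imputed patients.** Simulated Rubin pooling (100 imputations, 2 or 4 imputed patients, n = 26 to 34) rejected in 0.4% to 0.9% of trials at a true 10%. It covered 84% to 94% at true rates of 10%, 30% and 66%.

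**Zero width.** If 0/n or n/n respond in every imputation, both variance components are zero. For 0/6 the Wald interval is 0 to 0, while the Clopper-Pearson upper limit is 1 − 0.025^(1/6) = 46%. With six AS patients the chance of 0/6 or 6/6 is 0.9⁶ + 0.1⁶ = 53% at a true 10%, and 0.34⁶ + 0.66⁶ = 8% at 66%.

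**The case against.** The strongest reply is that Wald is inferred. The SAP never states the variance, and the two candidates err in opposite directions. That stands: the gap itself is certain, and the Wald consequences are conditional on that reading. It is the natural one, because Rubin's rules need an estimate with its standard error and SAP 4.3.1 ties the p-value to the interval. The null-variance reading fits that tie less well.

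A reader might infer that the one-sided 0.025 level is breached. Under the Wald reading it is not; the test is only harder to pass. A reader might also infer that the primary result is in jeopardy. At the 66% design rate it is not, and the power loss matters mainly at true rates near 25% to 30%. Nor is the change irregular: SAP 1.1.1 allows it, and the move to multiple imputation explains it, since an exact test does not supply the variance that Rubin's Rule needs.

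The subgroup point is limited too. SAP 3.8.1 and 3.8.2 call subgroup p-values exploratory, and the paediatric analyses are optional. In 3.8.1 the promise of a p-value and interval follows the 14-week endpoints, so its reach to responder rates is arguable.

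What remains is an unspecified variance in the success criterion, an interval that generally falls short of 95%, and no rule for 0% or 100%.

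**Conclusion.** The point holds as a specification gap with a modest cost, and it should be fixed. On the Wald reading, one extra responder is needed at n = 26-29 and 32-36 and none at n = 24-25, 30-31 and 37-38. At n = 28 this costs about 14 percentage points of power at a true 30% rate (78% to 64%) and almost nothing at the design rate. On the null-variance reading the 2.5% level would be exceeded at most sizes. The interval shortfall applies whatever the primary decision. Zero width arises only when none or all of a small group respond in every imputation. These conclusions rest on the assumed 24 to 38 patients aged 12 or over and on few imputed values. The documents do not support a claim that type I error is inflated or that the planned success is at risk.

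**What to change.** - Where no value is imputed, including most subgroups, use the protocol's exact binomial test and Clopper-Pearson interval at the SAP's one-sided 0.025 level.
- Where administratively missing values are imputed, name a small-sample pooling method that keeps p-value and interval consistent, such as Wilson-type limits combined under Rubin's rules, and state the rule for 0% and 100%. Tabulate its attained size at p0 = 10% first. With nothing imputed, a plain Wilson interval inverts the null-variance test, so without adjustment it would carry the 5.5% size shown for n = 28. If the chosen method exceeds 2.5%, let the exact analysis in the next item carry the decision.
- Report the exact test with administratively missing patients counted as non-responders, as a sensitivity analysis. It cannot exceed the nominal level.
- Apply the same rules to the hunger-responder endpoint.

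The cost is some SAP wording, a short size table, and a few lines of code beyond default PROC MIANALYZE output, all before unblinding. The non-responder analysis is slightly conservative.

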2. ANALYSIS POPULATION

2.1. Population Definitions

The following analysis populations will be evaluated and used for presentation and analysis of the data.

- Screening Analysis Set: All patients who signed the informed consent form.
- Safety Analysis (SA) Set: All patients who received at least 1 dose of study drug (placebo or setmelanotide). Analysis performed on the safety set will be based on patients according to treatment received.
- FAS: All patients (irrespective of age) who received at least 1 dose of setmelanotide and have baseline data.
- DUS: All patients in the FAS who demonstrate at least 5 kg weight loss (or at least 5% if baseline body weight is < 100 kg) over the first 14 weeks of active setmelanotide treatment, regardless of later disposition.

For any DUS analysis, the DUS subgroup includes:

- O Those patients initially randomized into the setmelanotide group in the double blinded, randomized, placebo-controlled period that achieved at least 5 kg weight loss (or at least 5% if baseline body weight is < 100 kg) from baseline at Week 15 visit.
- O Those patients who initially randomized in the placebo group in the double blinded, randomized, placebo-controlled period, and achieved at least 5 kg weight loss (or at least 5% if baseline body weight is < 100 kg) from week 15 (i.e., just prior to their first active dose of setmelanotide at week 15) through week 29 (i.e., after 14 weeks of active treatment with setmelanotide).
- PCS: All randomized patients who received at least 1 dose of placebo or setmelanotide and have baseline data. This population is specifically defined for the 14-week placebo-controlled, double-blind period (Period 1). Analysis performed on PCS will be based on subjects as randomized.
- Per-Protocol Set at End of Period 1 (PP at EOP1): All subjects in PCS without any major protocol violations that will result in exclusion of the subjects from the analysis.
- Per-Protocol Set at End of Period 2 (PP at EOP2): All subjects in FAS without any major protocol violations that will result in exclusion of the subjects from the analysis.
- Completers Set (CS): all subjects in the PP at EOP1 population who continue on active treatment or placebo to complete a full 14-week placebo-controlled double blinded period (Period 1)

The FAS population is the primary population for the analysis of efficacy endpoints. The DUS population may be used for sensitivity analyses of efficacy endpoints, as appropriate.

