4.3.2. Key Secondary Efficacy Analyses

Statistical testing will be performed on the key secondary efficacy endpoints according to the

following hierarchical order. Where applicable, the secondary endpoint will be compared against the null hypothesis for each of the 100 imputed datasets. The outcomes from the 100 imputed datasets will be combined using Rubin's Rule to provide a p-value and corresponding confidence interval as appropriate.

Body Weight Percent Change from Baseline in Patients ≥ 12 Years of Age:

Mean percent change from baseline in body weight for patients in the FAS population will be analyzed after ~52 weeks of treatment. Analyses will be based on a one-sample t-test for each of the 100 imputed datasets and assuming mean percent change from baseline in bodyweight of zero. The outcomes from the 100 imputed datasets will be combined using Rubin's Rule to provide a p-value and corresponding confidence intervals. This will be evaluated at a 1-sided, 0.025 significance level.

Sensitivity analysis based on the DUS population may be provided as needed.

Descriptive statistics for the change and percent change from baseline in body weight (kg) may be presented in the FAS population by active treatment visit.

Daily Hunger Score Percent Change from Baseline in Patients ≥ 12 Years of Age:

Mean percent change from baseline in the weekly average of the daily hunger scores for patients in FAS population will be analyzed after ~52 weeks of treatment. Analyses will be based on a one-sample t-test for each of the 100 imputed datasets with assumed mean percent change from baseline in weekly average of daily hunger scores of zero. The outcomes from the 100 imputed datasets will be combined using Rubin's Rule to provide a p-value and corresponding confidence intervals. This will be evaluated at a 1-sided, 0.025 significance level.

Prior to analysis, daily hunger scores for each of the 3 hunger assessments will be averaged separately by week. For a week of hunger scores to be considered evaluable, scores need to be recorded and available for analysis on at least 1 of 7 days to provide sufficient data to determine mean values.

Rhythm believes that the 1 out of 7 days approach will largely prevent missing data and best utilize the data points available. Unless specified otherwise, this will be applicable for all hunger score related analysis.

Sensitivity analysis based on the DUS population may be provided as needed.

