[figure not shown]
In order to look at the impact of missing hunger data, a sensitivity analysis may be done to examine if there are any differences in conclusions drawn by data availability; analysis for daily hunger scores will be repeated for patients with at least 3 of 7 days of data present. No imputations will be made for missing data.

[figure not shown]
Treatment Failure Analysis:

In order to look at the impact of missing data on the comparisons between setmelanotide-treated patients and placebo patients after ~14 weeks of treatment, a sensitivity failure analysis may be done. For the non-key, secondary endpoints, patients who have missing 14 week data will be considered treatment failures. Similar to the secondary analyses, this sensitivity analysis will be based on a two-sample t-test for each of the 100 imputed datasets. The outcomes from the 100 imputed datasets will be combined using Rubin's Rule to provide a p-value and corresponding confidence intervals.

Statistical Analysis Plan, Protocol RM-493-023 29 October 2020, Version 3.0

Table 3 Summary of Core Analysis Elements

Endpoints	Analysis Set (1) Primary (Sensitivity)	Main Patient Group	Baseline ⁽²⁾	Subgroup Analysis
Primary				
Proportion of patients who achieve a \geq 10% reduction from baseline in body weight after ~52 weeks of treatment	FAS (SH, AG, PP at EOP2)	≥12 years old	ATB	BBS, AS, <12 yo, <17 yo
Key Secondary (after ~52 weeks of treatment)				
Mean percent change from baseline in body weight	FAS (DUS)	≥12 years old	ATB	BBS, AS, <12 yo, <17 yo
Mean percent change from baseline in the weekly average of the daily hunger score	FAS (FAS: 3/7 daily	≥12 years old	ATB	BBS, AS, <12 yo
	responses, DUS)			
Proportion of patients who achieve a $\geq 25\%$ improvement in the weekly average of the daily hunger score	FAS (FAS: 3/7 daily responses)	≥12 years old	ATB	BBS, AS
Secondary (at the Week 14 visit)				
Mean percent change from baseline in body weight after treatment with setmelanotide as compared with placebo	PCS (PP at EOP1, CS)	≥12 years old	PCPB	BBS, AS, <12 yo, <17 yo
Mean percent change from baseline in the weekly average of the daily hunger score after treatment with setmelanotide as compared with placebo	PCS (PP at EOP1, CS, PCS: 3/7 daily responses)	>12 years old	PCPB	BBS, AS, <12 yo

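### The optional tests in the Designated Use Set take patients selected for early weight loss and compare them with an unselected 10% rate (or zero), so they do not hold their nominal level

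*SAP*

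**What the plan says.** SAP 2.1 builds the DUS from FAS patients who "demonstrate at least 5 kg weight loss (or at least 5% if baseline body weight is < 100 kg"), measured "over the first 14 weeks of active setmelanotide treatment, regardless of later disposition". For patients first randomised to placebo, the clock starts at Week 15. SAP 2.1 gives the set its role: "The DUS population may be used for sensitivity analyses of efficacy endpoints, as appropriate". It also says: "The FAS population is the primary population for the analysis of efficacy endpoints".

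SAP 4.3.1 sets out the primary test, H0: response rate at most 10%, at one-sided 0.025, and adds: "This analysis may be repeated on the following analysis sets: DUS, PP at EOP2, SH, AG, as appropriate". It gives no other reference rate for the DUS.

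SAP 4.3.2 says, under both mean percent change endpoints (body weight and hunger score): "Sensitivity analysis based on the DUS population may be provided as needed". The main test there is a one-sample t-test against zero.

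Table 3 lists DUS as a sensitivity set for those two mean-change endpoints. For the primary endpoint it lists only "FAS (SH, AG, PP at EOP2"), so it disagrees with 4.3.1.

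The 10% comes from the protocol synopsis (Statistical Considerations). There a registry figure of 6.4% for spontaneous loss of at least 10% over one year, in patients aged 12 or older, is rounded up to be conservative. No condition on early loss is described.

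**The concern.** Both the DUS rule and the one-year endpoint are read from the same patient's weight against the same active-treatment baseline (SAP 3.4). A patient who is already 5% down at 14 weeks, for whatever reason, is more likely than average to be 10% down at one year. Untreated patients picked in the same way would exceed 10% too. The 10% rate describes everyone; the DUS describes those who started well.

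The t-test of mean weight change against zero has the same defect. For hunger the effect is indirect: it arises only as far as hunger change tracks weight loss.

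A sensitivity analysis asks whether the main result survives a change in an assumption. Selecting on early outcome does not ask that question. At stake is a p-value, labelled as sensitivity, that falls below 0.025 more often than 2.5% of the time when the drug adds nothing to the historical rate. No text in the SAP warns of this or limits the DUS to description.

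**Working it through.** **The plan's own figure.** The documents give no figure for the DUS. The only stated figure for this test is power with n=7, 10% against 66%: about 95% at one-sided 0.05 and about 91% at 0.025. The arcsine formula gives 95.3% and 91.2%. The exact test gives 95.1% at 0.05 (3 or more of 7) and 81.6% at 0.025 (4 or more of 7). This confirms only that the null and the test are read as intended.

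**Inputs from the documents.** Null rate 10%; registry rate 6.4%; one-sided 0.025; pivotal cohort 38 (SAP 1.1.1; the number aged 12 or older is not given).

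**Assumptions.** Percent changes at 14 and 52 weeks are bivariate normal with correlation ρ of 0.5 to 0.7. The 14-week SD is 0.52 to 0.60 of the 52-week SD. The mean 52-week change is 0 to +1%, pro-rated at 14 weeks (1 × 14/52 = 0.27%). The entry rule is taken as 5%. N aged 12 or older is 25 to 38.

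**Step 1: response rate inside the DUS with no drug effect.** SD52 = (10 + mean)/1.2816, so that 10% of patients lose at least 10%. SD14 = ratio × SD52. The qualifying share is s = Φ((−5 − mean14)/SD14). The DUS rate is c = P(both criteria met)/s.

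**Step 2: rejection rate.** For a DUS of size m, reject at r(m) responders, the smallest count with P(X ≥ r | m, 10%) ≤ 0.025 (for example 3 when m is 4, 5 or 6). Then average P(X ≥ r(m) | m, c) over m ~ Binomial(N, s).

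| Mean | Ratio | ρ | SD52 | SD14 | s | P(both) | c | Rejects, N=25 | Rejects, N=38 |
|---|---|---|---|---|---|---|---|---|---|
| 0 | 0.52 | 0.5 | 7.80 | 4.06 | 10.9% | 3.4% | 32% | 7.5% | 12.6% |
| 0 | 0.52 | 0.7 | 7.80 | 4.06 | 10.9% | 4.9% | 45% | 17.1% | 28.5% |
| 0 | 0.60 | 0.5 | 7.80 | 4.68 | 14.3% | 4.1% | 29% | 8.5% | 14.1% |
| 0 | 0.60 | 0.7 | 7.80 | 4.68 | 14.3% | 5.8% | 40% | 18.7% | 30.8% |
| +1% | 0.60 | 0.5 | 8.58 | 5.15 | 15.3% | 4.3% | 28% | 8.8% | 14.4% |
| +1% | 0.60 | 0.7 | 8.58 | 5.15 | 15.3% | 6.0% | 39% | 19.0% | 31.1% |

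So c is about 28% to 45% and rejection about 8% to 31%. With 6.4% overall, the same steps give c of 23% to 40% and rejection of about 3% to 15%. In the unselected FAS at a true 10%, the exact test rejects 0.8% (N=30) to 1.1% (N=38) of the time.

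**Step 3: the 5 kg rule.** Above 100 kg the rule is looser than 5%: 5/120 = 4.2% and 5/150 = 3.3%. The DUS rate becomes about 26% to 40% at 120 kg and 24% to 34% at 150 kg. Rejection at 120 kg is about 9% to 31%, nearly unchanged.

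**Step 4: mean change.** With mean 0 and ratio 0.60, the expected 52-week change in the DUS with no effect is −ρ × SD52 × φ(1.068)/Φ(−1.068) = −ρ × 7.80 × 0.2255/0.143 = −ρ × 12.3. That is about −6% at ρ = 0.5 and −9% at ρ = 0.7, while the test assumes zero.

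**Wider assumptions.** Fixing s at 10% to 30% directly, with ρ from 0.3 to 0.8 and N of 30 to 38, gives a DUS rate of 17% to 56% and rejection of 3.3% to 43%. The bias vanishes only at ρ = 0.

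**The case against.** Nothing confirmatory depends on the DUS. Every use is permissive, SAP 4.3 calls these analyses supportive, and success is judged in the FAS. The missing-data sensitivity analyses in SAP 4.3.4 (non-replacement and active-treatment completers) do not use it. All of this stands and keeps the point minor.

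Three stronger readings are tempting, and the documents support none of them.

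- A reader might infer that the DUS test would reject 35% to 87% of the time with no effect. Those are the exact-test results for 10 to 20 patients at a 30% or 40% rate (35% and 58%; 62% and 87%). But under the same no-effect model only 11% to 15% of patients qualify, about 4 to 6 of 38, and the chance of 10 or more is about 0.6% to 6%. Averaging over the DUS size is the right summary.
- A reader might infer that the DUS result can only look better than the FAS result. It need not. Dropouts after week 14 stay in the set, and those whose 52-week value is missing for non-administrative reasons count as failures (SAP 3.10.2). The set is also smaller, so its p-value can be the larger one. The upward bias is in expectation.
- A reader might infer that the sponsor will use the DUS to support the primary conclusion. The SAP uses the word sensitivity but does not say that.

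The correlation and SD ratio are assumed, and the SAP combines proportions by Rubin's rule rather than using an exact test. The exact rejection rates may therefore differ somewhat; the direction does not depend on this.

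**Conclusion.** The concern holds as a minor one. The DUS is selected on early outcome, and repeating the test against 10%, or the weight-change test against zero, in that set gives an estimate biased upward in expectation and a test above its nominal level. Under the stated assumptions the no-effect response rate in the DUS is about 28% to 45%, and rejection about 8% to 31% against a nominal 2.5% (23% to 40% and about 3% to 15% at the registry rate). Failures among later dropouts soften the bias but do not remove it. The primary analysis and the trial's type I error are unaffected. Separately, and without any assumption, SAP 4.3.1 and Table 3 disagree on whether DUS applies to the primary endpoint.

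**What to change.** Make four edits to the SAP:

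- Delete DUS from the sets on which the primary test is repeated in 4.3.1. This also brings 4.3.1 into line with Table 3.
- Remove the DUS sensitivity tests from 4.3.2.
- Remove DUS from the two mean-change key secondary rows of Table 3.
- Change the sentence in 2.1 that offers DUS for sensitivity analyses.

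Report DUS descriptively instead, labelled as outcome among early responders: number of patients, share of the FAS that qualified, estimate and confidence interval, with no p-value. This still shows how patients with early weight loss fare at one year.

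The cost is wording and a column in optional tables. Data collection, conduct and the primary analysis do not change. The sponsor gives up an optional supportive p-value.
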